Project title:

Use of Diced Cartilage for Management of Internal Mammary Vessel Exposure Sites in
Autologous Breast Reconstruction

Date: 10.07.2024

1) Studyprotocol

Procedures for informing and obtaining consent:

The recruited subjects will be informed about the nature, importance, risks (anonymizes data management) and scope of the intended scientific investigation in a personal conversation with one of the investigators and will receive patient information. After sufficient time for reflection, the consent will be confirmed in writing on the form prepared for this purpose - declaration of consent.

Measures:

This retrospective single-center cohort study included all autologous breast reconstructions performed from October 2021 to June 2023, in which diced cartilage (DC) was used to manage internal mammary vessel exposure sites (IMVES). These reconstructions will be divided into two groups: one with prior ipsilateral breast radiotherapy (DCR) and one without irradiation (DC) to evaluate the suitability of irradiated cartilage for the DC procedure. The control group consisted of an equal number of consecutive autologous breast reconstructions performed before the implementation of the DC procedure, for which rib cartilage segments were also removed but IMVES were managed conservatively. Controls will not be recruited during the period of DC use because initially, DC was not used consistently by all team members and may have been avoided in difficult reconstructions limiting the comparability of these patients. Data will be collected using electronic patient records, photographic documentation, and available postoperative MRI of reconstructed breasts.

Magnetic resonance imaging (MRI) scans performed at least 6 months postoperatively will be used to evaluate the sinking depth of epicostal soft tissue into the space of rib segment resection on axial planes (JiveX Software, VISUS Health IT GmbH, Bochum, Germany).

Postoperative photographic images will be examined by two investigators (blinded to group assignments) for IMVES-associated deformities using standardized photographic images of the reconstructed breasts at the 6-month follow-up.

2) Statistical Analysis Plan

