Statistical analysis will be performed using IBM SPSS Version 24 (IBM, Somers, NY, USA) and R 4.3.2 (R Core Team). Metrically scaled parameters will be assessed for a normal distribution using Shapiro–Wilk tests. Results for normal data will be presented as mean \pm standard deviation (SD) and will be analyzed using multi-factor variance analysis. Paired t-tests with Bonferroni correction will be used when significant differences were observed. Non-normally distributed metric parameters will be expressed as median (Q25–Q75) values and will be assessed using the Kruskal–Wallis test. Pairwise Mann–Whitney U tests with the Bonferroni correction will be used when significant differences were found. Categorical parameters will be assessed using the Chi-squared or Fisher tests, without tests for normality. Pairwise chi-square tests (or Fisher tests) with Bonferroni correction will be used when significant results were found. MRI data will be analyzed by isolating subgroups of the study population with MRI and applying pairwise case exclusions. A Chi-square test of independence will be performed to determine whether the groups differed significantly with regard to the presence of MRI. In addition, further comparison of the three groups will be carried out for the variables surveyed to clarify group differences. The significance level will be set at $\alpha = 0.05$ for all tests.

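### The SAP makes no provision for unequal variances although its control rule makes the groups unequal in size; specifying Welch tests is a nearly free improvement

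*Combined protocol and SAP*

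**What the plan says.** In the Statistical Analysis Plan, the only distributional check is on shape: "Metrically scaled parameters will be assessed for a normal distribution using Shapiro–Wilk tests". Outcomes that pass "will be analyzed using multi-factor variance analysis", with factors that are not named. The follow-up is: "Paired t-tests with Bonferroni correction will be used when significant differences were observed". Non-normal outcomes go to Kruskal–Wallis and Mann–Whitney tests. The significance level is 0.05 for all tests. Neither part of the document mentions a check of equal variances, a Welch-type test or robust standard errors.

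The group sizes follow from the Measures text of the study protocol. The study "included all autologous breast reconstructions performed from October 2021 to June 2023" in which diced cartilage was used, and divides these by prior ipsilateral radiotherapy into DCR (irradiated) and DC (not irradiated). Then: "The control group consisted of an equal number of consecutive autologous breast reconstructions performed before the implementation of the DC procedure". Sinking depth is analysed only in the patients who have an MRI. No group size, SD or expected difference is stated.

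**The concern.** Classical ANOVA and the pooled t-test assume the same variance in every group. With similar group sizes a breach does little harm. With unequal sizes the error rate moves, and its direction depends on which group has the larger spread. If a small group is the more variable, the pooled variance is too small for comparisons with that group and false positives rise. If the large control group is the more variable, the test becomes too strict and real differences are missed.

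The control rule removes the protection of similar sizes. The comparison most exposed is DCR against control whenever DCR is the smallest group, and the suitability of irradiated cartilage is a question that the protocol singles out. Unequal spread is plausible: a filled resection gap may limit sinking depth while an unfilled gap does not, and irradiated cartilage may behave less uniformly. That is reasoning only; the documents contain no data on it.

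**Working it through.** **Inputs from the documents.** Significance level 0.05. Three groups, hence three pairwise comparisons, so the Bonferroni level is 0.05/3 = 0.0167. Pairwise tests follow only a significant overall test. On the natural reading n(control) = n(DC) + n(DCR), so an even split gives 1:1:2 and any other split is more uneven.

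**Assumed inputs.** Sizes DC/DCR/control of 30/30/60 (the best case, 1:1:2) and 40/20/60; SD ratios of 1, 1.5 and 2 in either direction; normal data; equal means; one factor. The follow-up t-tests are read as unpaired pairwise tests, because the groups are independent and of different sizes.

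**The plan's own figure.** With equal variances the simulated ANOVA error is 4.9–5.1% at all sizes tried, so the nominal 5% is reproduced.

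**A check by hand: DCR against control, pooled t-test, large samples.** Let DCR have m patients and control r·m. Then

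- true variance of the difference = (SD_C²/r + SD_DCR²)/m
- variance that the pooled test uses = [(r·SD_C² + SD_DCR²)/(r + 1)]·(1/r + 1)/m
- actual error = 2·(1 − Φ(z·√(used/true)))

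where z = 1.960 at 0.05 and 2.394 at 0.0167.

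*r = 2 (30 v 60), DCR SD doubled.* True = 1/2 + 4 = 4.5; used = (2 + 4)/3 × 1.5 = 3.0; √(3.0/4.5) = 0.816. Error is 11.0% at the 0.05 level and 5.1% at the 0.0167 level.

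*r = 2, control SD doubled.* True = 4/2 + 1 = 3.0; used = (8 + 1)/3 × 1.5 = 4.5; √(4.5/3.0) = 1.225. Error is 1.6% and 0.3%.

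*r = 3 (20 v 60), DCR SD doubled.* True = 1/3 + 4 = 4.33; used = (3 + 4)/4 × 1.333 = 2.33; ratio 0.538, root 0.734. Error is 15.0% and 7.9%.

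*r = 3, control SD doubled.* The two variances swap; ratio 1.857, root 1.363. Error is 0.8% and 0.1%.

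**Simulation of the planned sequence.** The last column requires a significant ANOVA and then a pairwise result at 0.0167; the intended rate there is at most 1.67%.

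| DC/DCR/control | More variable group (SD ratio) | ANOVA, nominal 5% | Welch ANOVA | DCR v control, after gate and Bonferroni |
|---|---|---|---|---|
| 30/30/60 | DCR (2) | about 10% | about 5% | about 5% |
| 30/30/60 | control (2) | about 2% | about 5% | about 0.4% |
| 40/20/60 | DCR (2) | about 14% | about 5% | about 8% |
| 40/20/60 | control (2) | about 2% | about 5% | about 0.1% |

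With an SD ratio of 1.5, ANOVA error is about 7% (30/30/60) or 9% (40/20/60) when DCR is the more variable, and about 3% when control is. Sizes of 16/8/24 give nearly the same results as 40/20/60. With equal group sizes, ANOVA stays at 5.1–7.4% even with SD ratios up to 3, so it is the imbalance that creates the sensitivity.

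**Power, DCR v control, 40/20/60, control mean an assumed 0.7 SD higher, after gate and Bonferroni.** Control SD 1.5 times larger: 27–29% with classical tests against 46% with Welch tests. Control SD twice as large: 11–12% against 35%. Equal variances: 61% against 58%.

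**The case against.** The strongest reply is that the documents do not show unequal spread. The suggested mechanisms point in opposite directions: a more variable control group lowers the error, a more variable DCR group raises it. This stands. It means that the size and direction of any distortion in this study are unknown. It does not remove the gap, because the plan has no safeguard for either case.

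A reader might infer that the plan's tests run at anything from 1% to 15% instead of 5%. The documents do not support that. Such a range needs an assumed SD ratio and an assumed DC/DCR split. In the simulations ANOVA did not fall below about 1.7%, even with SD ratios up to 3. The values near 1% and 15% belong to an ungated pooled t-test at 0.05, which the plan does not run, since its pairwise tests are gated and Bonferroni-corrected.

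Three further points stand in part.

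- The SAP's wording is paired t-tests. A truly paired test needs no equal-variance assumption, but it does not fit independent groups. The t-test figures therefore hold only if unpaired pairwise tests are meant, and even then the plan does not say that variances are pooled.
- Group sizes for sinking depth depend on who has an MRI, not on the control rule. Imbalance there is not certain, but balance is not assured either.
- Outcomes sent to the rank tests are less affected: Kruskal–Wallis gives about 8% or 3% at 1:1:2 when control and the two treated groups differ by an SD ratio of 2.

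**Conclusion.** The concern holds as a cheap improvement, not as a demonstrated error in the results. The documents establish that only normality is screened, that no method for unequal variances is named, and that on the natural reading control is larger than either treated group. The consequence depends on unstated SDs and an unstated split. With an SD ratio of 2, ANOVA error is about 10% or 2% at the most favourable sizes, and the gated, Bonferroni-corrected rate for DCR against control is about 5–8% or 0.1–0.4% against an intended 1.67%. These figures assume normal data, one factor and unpaired follow-up tests. The factors in the plan's multi-factor model are unnamed, so that model could not be simulated.

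**What to change.** Amend the Statistical Analysis Plan for normally distributed metric outcomes:

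- Use Welch's ANOVA for the three-group comparison.
- Use Bonferroni-corrected Welch two-sample t-tests, with Welch confidence intervals, for the pairwise comparisons. This also replaces the reference to paired tests.
- Apply both always, without a preliminary test of variances.
- Welch's ANOVA covers only the one-way comparison. If a multi-factor model is fitted, name its factors and use heteroscedasticity-robust (HC3) standard errors.

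The rank-based tests can stay as planned. Brunner–Munzel is an option only where groups are not very small: at 8 v 24 with equal variances its error at the Bonferroni level was about 2.8% against 1.67%.

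The cost is SAP wording, and R is already named as software. In the simulations the Welch ANOVA and Welch t-tests stayed close to their nominal level whether or not the variances were equal. If the variances are in fact equal, gated power for DCR against control falls from about 61% to 58% (40/20/60, assumed difference 0.7 SD).

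### The SAP names paired t-tests as the post-hoc test for normally distributed outcomes, but the design defines no pairing between the DC, DCR and control groups

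*Combined protocol and SAP*

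**What the plan says.** Section 2 (Statistical Analysis Plan) sets out three routes for comparing the groups.

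- Normally distributed metric outcomes "will be analyzed using multi-factor variance analysis". The follow-up rule is "Paired t-tests with Bonferroni correction will be used when significant differences were observed".
- Non-normal metric outcomes go to Kruskal–Wallis, and then "Pairwise Mann–Whitney U tests with the Bonferroni correction will be used when significant differences were found".
- Categorical outcomes go to chi-squared or Fisher tests, and then "Pairwise chi-square tests (or Fisher tests) with Bonferroni correction will be used when significant results were found".

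The groups are defined in section 1 (Studyprotocol), under Measures. Of the diced-cartilage reconstructions it says "These reconstructions will be divided into two groups: one with prior ipsilateral breast radiotherapy (DCR) and one without irradiation (DC"). Of the controls it says "The control group consisted of an equal number of consecutive autologous breast reconstructions performed before the implementation of the DC procedure".

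MRI sinking depth comes from "available postoperative MRI of reconstructed breasts", and the SAP adds that "MRI data will be analyzed by isolating subgroups of the study population with MRI and applying pairwise case exclusions".

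**The concern.** A paired t-test analyses within-pair differences, so it needs a rule saying which observation in one group belongs with which in the other. Neither section gives one. DC and DCR come from splitting one series on radiotherapy history, and the controls come from an earlier period. An equal count is not a match, and no matching variable, linkage or repeated measurement is described.

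The SAP is also inconsistent with itself. For the same contrasts, an outcome would be treated as paired or independent depending only on its Shapiro–Wilk result.

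If the rule were followed as written, the post-hoc p-value would depend on row order, and cases without a partner would be dropped. If the word is only a slip, the plan of record names a different test from the one meant, and a report using the right test would formally depart from the plan.

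**Working it through.** **Is there any pairing in the design?**

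| Contrast | How the groups arise | Link between individual observations |
|---|---|---|
| DC v DCR | Split on prior ipsilateral irradiation | None defined |
| DC v control | Later v earlier period | None defined |
| DCR v control | Later v earlier period | None defined |

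The unit is the reconstruction, so one patient could contribute an irradiated and a non-irradiated breast. The documents mention no bilateral cases. Any such pairs would cover only part of DC v DCR and would not support a paired test across all three contrasts.

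**Do the numbers allow pairing?** The natural reading of the control definition is n(control) = n(DC) + n(DCR). If both subgroups are non-empty, controls outnumber each of them, and pairing one to one means discarding controls. Nothing makes DC and DCR equal in size. In the MRI subgroups, equal numbers are not assured on any reading.

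**What would the literal reading cost?** The plan states no sample size, SD, effect or power, so there is no figure to reproduce. The following is illustration with assumed inputs: unrelated normal samples, two-sided tests (the SAP does not state sidedness), three contrasts, and a level of 0.05/3 = 0.0167 per contrast.

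*Type I error.* Arbitrary pairing of unrelated samples, 200,000 runs in each of seven size and SD settings (from 30 v 30 to 12 v 40, SD ratios from 1:2 to 2:1), gave 0.0166 to 0.0168. This is nominal. Family-wise error of the whole procedure (F test at 0.05, then Bonferroni, all means equal, 100,000 runs), literal paired v Welch:

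- Sizes 30/30/30, equal SDs: 0.035 v 0.040
- Sizes 30/30/60, equal SDs: 0.026 v 0.037
- Sizes 30/30/60, SDs 2/1/1: 0.030 v 0.031

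*Power at d = 0.6.* The independent test has noncentrality d·√(n₁n₂/(n₁+n₂)) on n₁+n₂−2 degrees of freedom. Arbitrary pairing of m unrelated pairs has noncentrality d·√(m/2) on m−1.

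- 30 v 30: both noncentralities are 0.6·√15 = 2.324. Independent, 58 df, critical t 2.465: power 45% (Welch, simulated, also 45%). Paired, 29 df, critical t 2.541: power 43%.
- 30 v 60: independent noncentrality 0.6·√20 = 2.683, 88 df, critical t 2.441: power 60% (Welch, simulated, 59%). Paired, with half the larger group dropped: 43%, as above.

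Under the natural reading of the control count, 30 v 30 could describe only DC v DCR, and only if those happen to be equal. The 30 v 60 case is then control v either subgroup, since 30 + 30 = 60.

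*Dependence on row order, 30 v 30.* 300 data sets were scaled to an exact standardised difference, with 2,000 random pairings of each.

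| Observed difference | t = difference·√15 | Independent p (58 df) | Paired p, middle 95% (average) | Pairings below 0.0167 |
|---|---|---|---|---|
| 0.60 | 2.324 | 0.024 | 0.007 to 0.056 | 19% |
| 0.65 | 2.517 | 0.015 | 0.004 to 0.039 | 46% |

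Both differences sit close to the threshold. A less selected measure uses a true d of 0.6 and asks how often pairing order really matters, meaning that between 5% and 95% of 1,000 random pairings are significant. This held in 28% of 2,000 data sets at 30 v 30 and in about 70% at 30 v 60.

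**The case against.** The strongest reply is that this is one wrong word. Every other comparison the SAP names for these groups is an independent-samples procedure, and the two neighbouring post-hoc rules say pairwise. A competent analyst would very likely read this one the same way, and then no result changes. The order-dependence figures describe an analysis that was probably never meant, and the table uses near-threshold examples, where any perturbation flips verdicts. The literal reading would also tend to expose itself: a paired routine given 30 and 50 values stopped with an error.

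Most of this stands, and it limits the weight of the point. It does not remove it. The paired t-test is a valid procedure in its own right, not an impossible name, and the word sits in the sentence that decides which test is run. Unequal lengths do not guarantee discovery, since software that drops incomplete rows would return a result. An edit to the rule is needed on either reading.

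**Conclusion.** The concern holds. The stated post-hoc test does not fit the design, and nothing in the documents corrects it. It is probably a slip for pairwise, though the documents do not confirm that.

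The reach is narrow: metric outcomes that pass Shapiro–Wilk and then give a significant variance analysis. MRI sinking depth could be one of them. Omnibus tests, non-normal outcomes and categorical outcomes are unaffected, and no figure in the plan changes.

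On the literal reading, the harm is a verdict that depends on arbitrary row order, plus lost power: about 2 percentage points at equal sizes, and about 16 at 30 v 60 (59% to 43%), where the discarded cases make the problem hard to miss. False-positive error is not inflated. These magnitudes rest wholly on assumed sizes, SDs and effects. The mismatch between test and design does not. The point should be fixed, with high confidence, as a small correction.

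**What to change.** In section 2, replace the paired t-tests with pairwise independent-samples comparisons between the three groups, Bonferroni corrected. Two forms are suitable:

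- contrasts from the fitted variance-analysis model, which suit a multi-factor analysis; or
- independent-samples t-tests where group is the only factor, preferably in Welch form.

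The choice between these, and any robust standard errors for model contrasts, is optional; naming an independent-samples comparison is not. If a pairing was in fact intended, the plan should define it. If the analysis has already been run, state which test was used.

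The cost is one sentence and no new data. The Bonferroni level stays at 0.0167 for three contrasts. The Welch form costs almost nothing when SDs are equal: 59% v 60% power against the pooled test at an assumed 30 v 60 and d = 0.6. Clustering of two breasts within one patient would bear on every test in the plan and is a separate matter.

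### With three groups and a significant overall test required first, the added Bonferroni correction is not needed to hold 5% familywise error per variable and costs power

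*Combined protocol and SAP*

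**What the plan says.** Section 2) Statistical Analysis Plan has three branches, each an overall test followed by conditional, corrected pairwise tests.

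- Normal metric data, after a multi-factor analysis of variance: "Paired t-tests with Bonferroni correction will be used when significant differences were observed".
- Non-normal metric data, after a Kruskal–Wallis test: "Pairwise Mann–Whitney U tests with the Bonferroni correction will be used when significant differences were found".
- Categorical data, after a chi-squared or Fisher test: "Pairwise chi-square tests (or Fisher tests) with Bonferroni correction will be used when significant results were found".

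The level is common to all: "The significance level will be set at $\alpha = 0.05$ for all tests". The same section confirms the number of groups: "further comparison of the three groups will be carried out for the variables surveyed to clarify group differences". Section 1) Studyprotocol, under Measures, defines them. The diced-cartilage reconstructions are split into "one with prior ipsilateral breast radiotherapy (DCR) and one without irradiation (DC"), and "The control group consisted of an equal number of consecutive autologous breast reconstructions performed before the implementation of the DC procedure".

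The SAP gives no reason for combining the gate with the correction. It also gives no Bonferroni divisor, primary endpoint, adjustment across variables, sample size or power calculation.

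**The concern.** The gate and the Bonferroni divisor both deal with the same multiplicity, the three pairwise comparisons within one variable. With four or more groups a gate alone would not be enough. With exactly three it is, provided that it tests the three-group effect.

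Power is at stake. The cohort is retrospective and bounded by calendar dates, and MRI outcomes exist only for patients who were scanned, so lost power cannot be recovered by recruiting. The comparison of DCR with DC is exposed in particular: it is the stated reason for splitting the diced-cartilage cases and, if controls equal DC and DCR combined, it sets the two smaller groups against each other.

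**Working it through.** **Inputs.** From the documents: alpha 0.05 for every test; three groups, hence three pairs. Assumed, because not stated: two-sided tests; Bonferroni divisor 3, so 0.05/3 = 0.0167; controls equal in number to DC and DCR combined, with an even DC/DCR split, so control/DC/DCR are 2:1:1 (3:2:1 and 1:1:1 were also tried); effects of 0.6 SD, or event rates of 0.40 against 0.10. Independent-samples t-tests were used in place of the paired tests that the SAP names. The plan has no power figure to reproduce.

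**Step 1: why the gate is enough.** Write the pairwise nulls as C=D, C=R and D=R (control, DC, DCR). If any two hold, the third follows, so every intersection of pairwise nulls is the global null C=D=R. Closed testing therefore rejects a pair when the overall test and that pair's own test are both significant at 0.05.

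- All groups equal: a false positive requires the gate to open, so the error is at most 0.05.
- Exactly one pair equal: a false positive requires that one test to reject, so the error is at most 0.05.
- Exactly two pairs equal: impossible.

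With no gate, three unadjusted tests would give 1 − 0.95³ = 0.143 if independent, and about 0.12 with the actual correlation. The gate brings this down to 0.05.

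**Step 2: realised familywise error per variable (simulation).**

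| Tests | Truth | Gate + Bonferroni | Gate + 0.05 |
|---|---|---|---|
| ANOVA/t and chi-square | no groups differ | 3.8–4.1% | 4.9–5.2% |
| ANOVA/t and chi-square | one group differs | 0.3–1.8% | 3.6–5.4% |
| Kruskal–Wallis/Mann–Whitney | no groups differ | 3.2–3.6% | 4.2–4.7% |
| Kruskal–Wallis/Mann–Whitney | one group differs | 1.3–1.9% | 4.1–5.4% |

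Values just above 5% reflect simulation noise or the chi-square approximation, which can run slightly high when events are few. They do not come from the gating.

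**Step 3: power without the gate, by formula.** Large-sample power is Φ(d/√(1/n₁ + 1/n₂) − z), with z = 1.960 at 0.05 and 2.394 at 0.0167.

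- Control v DC, 60 v 30, d = 0.6: 0.6/√(1/60 + 1/30) = 0.6/0.2236 = 2.683. Power is Φ(0.723) = 0.765 at 0.05 and Φ(0.289) = 0.614 at 0.0167.
- DCR v DC, 30 v 30, d = 0.6: 0.6/√(2/30) = 0.6/0.2582 = 2.324. Power is Φ(0.364) = 0.642 at 0.05 and Φ(−0.070) = 0.472 at 0.0167.

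**Step 4: power with the gate (simulation).**

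| Control/DC/DCR | Pattern | Contrast | Gate + Bonferroni | Gate + 0.05 | Gain (points) |
|---|---|---|---|---|---|
| 60/30/30 | 0.6 SD in DC and DCR | control v DC | 59.7% | 72.0% | 12 |
| 80/40/40 | 0.6 SD in DC and DCR | control v DC | 75% | 85% | 10 |
| 60/30/30 | 0.6 SD in DC only | DCR v DC | about 44% | about 57% | 13 |
| 60/30/30 | 0.40 v 0.10 in both | control v DC | 75.4% | 88.1% | 13 |
| 40/20/20 | 0.40 v 0.10 in both | control v DC | 50.4% | 70.1% | 20 |

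The gain for control v DC at 2:1:1 is smaller in other patterns: 5–8 points when only DC differs and 4–6 when effects are graded across the groups. Across the scenarios tried it runs from about 2 to 20 points, and is near 0 when power is close to 1.

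**Step 5: Holm without a gate.** Holm rejects every pair that Bonferroni rejects, and so every pair that gated Bonferroni rejects. It holds 5% familywise error whatever opens the gate. At 60/30/30 with 0.6 SD in both groups, power for control v DC is about 59% under the current rule, 63% with Holm and 72% with gated unadjusted tests.

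**The case against.** The strongest objection concerns the ANOVA branch. The SAP names neither the factors of the multi-factor model nor the effect whose significance opens the pairwise tests. If another factor could open the gate, the closed-testing argument fails: unadjusted pairwise error could approach the ungated 12%, and Bonferroni would be the only protection. Pairwise tests on raw means also need not address the same hypotheses as a group effect adjusted for unbalanced factors. This objection stands and limits the fix. A reader might infer that Bonferroni is redundant in all three branches; the text supports that only for the Kruskal–Wallis and chi-squared/Fisher branches.

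A reader might also infer that the correction brings no error-rate benefit. Step 2 shows otherwise: false positives for a remaining true-null pair fall about threefold. The SAP does not state a 5% familywise target per variable, has no primary endpoint, and tests several variables without adjustment in a historically controlled study. A stricter pairwise threshold is a defensible cautious choice. It is not, however, a correction for multiplicity across variables, which would need its own rule.

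Finally, the document is dated 10.07.2024 and the last reconstructions were in June 2023, so the 6-month photographs probably already existed. Relaxing a threshold at that stage could look data-driven unless its timing is recorded.

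**Conclusion.** The point holds as an efficiency improvement. With three groups and a 0.05 gate on the group effect, Bonferroni is valid but not needed to keep familywise error at 5% per variable. It makes the procedure conservative, at about 4% under the global null and about 1.6% for a remaining true-null pair, where about 5% is allowed.

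The usual cost of 10 to 13 points applies to moderate-power scenarios at 2:1:1, for control v DC or DCR when both differ from control, and for DCR v DC when only DC differs. It should not be read as a property of this study, because sizes, split and effects are all assumed. Nor should the point be read as a finding of error: nothing in this step inflates type I error.

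**What to change.** 1. **Kruskal–Wallis and chi-squared/Fisher branches:** keep the overall test at 0.05 as the gate, run the three pairwise tests at 0.05 without Bonferroni, and state that this is closed testing for three groups.
2. **ANOVA branch:** do the same only if the SAP states that the gate is the test of the three-group effect and that the pairwise comparisons are independent-group contrasts from the same model.
3. **Otherwise, or for all branches if one rule is preferred:** replace gated Bonferroni with Holm across the three pairs, without a gate. It is never less powerful than the current rule, holds 5% familywise error, needs no gate definition, and gains about 2 to 5 points in the continuous scenarios above.
4. Record in the SAP, with a date, that the change was made before any group comparison was run.

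The cost is a revision of three sentences, plus a definition of the ANOVA gate if option 2 is used. No further data are needed. Options 1 and 2 give up the extra conservatism: realised error per variable rises to about 5%.

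### The one check aimed at the MRI subset compares scan rates between groups, so it need not detect outcome-related scanning and a biased sinking-depth comparison can pass it

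*Combined protocol and SAP*

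**What the plan says.** Under Measures in the Studyprotocol section, the sources are existing records: "Data will be collected using electronic patient records, photographic documentation, and available postoperative MRI of reconstructed breasts". The depth outcome is defined on those scans: "Magnetic resonance imaging (MRI) scans performed at least 6 months postoperatively will be used to evaluate the sinking depth". There is no upper time limit, no scheduled scan and no plan to record why a scan was done.

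The Statistical Analysis Plan then restricts the analysis: "MRI data will be analyzed by isolating subgroups of the study population with MRI and applying pairwise case exclusions". It follows with the check: "A Chi-square test of independence will be performed to determine whether the groups differed significantly with regard to the presence of MRI". It does not say what follows from either result.

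The next sentence adds that "further comparison of the three groups will be carried out for the variables surveyed to clarify group differences". The plan has no comparison of scanned with unscanned breasts, no weighting, imputation or adjustment for who was scanned, and no sensitivity analysis.

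**The concern.** The depth comparison depends on which breasts were scanned. It is distorted when scanned breasts differ from unscanned ones within a group and do so differently between groups. It can also be distorted when one shared scanning pattern acts on groups that truly differ. A table of group by MRI yes/no holds no outcome or case-mix data, so it cannot distinguish harmless from harmful selection when the rates are similar. If the rates differ and the test flags this, it does not show why.

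Sinking depth is the only continuous outcome that the documents name. The controls come from before DC was introduced, so follow-up time and imaging practice could differ between groups. The protocol already plans a blinded reading of 6-month photographs that is not tied to MRI. That reading could show whether scanned breasts differ in outcome, but the plan does not use it for this purpose.

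**Working it through.** The documents give no sample size, scan rate, SD or effect size, so there is no planned figure to reproduce. Every input below is an assumption, chosen to show the mechanism.

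**Arithmetic example.** Sinking is 8 mm if the breast is deformed and 3 mm if not. One third of controls and 10% of DC breasts are deformed. Mean depth = 3 + 5 × proportion deformed.

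- True means: control 3 + 5 × 1/3 = 4.67 mm; DC 3 + 5 × 0.10 = 3.50 mm. True difference 1.17 mm.
- *Scanning depends on outcome in controls only* (probability 0.6 if deformed, 0.3 if not; DC 0.4 throughout). Control scan rate = 1/3 × 0.6 + 2/3 × 0.3 = 0.40. Deformed among scanned controls = 0.20/0.40 = 0.50, so their mean is 5.50 mm. Observed difference 5.50 − 3.50 = 2.00 mm; 2.00/1.17 = 1.71, or 71% too large. Scan rates are 40% v 40%.
- *Same 0.6/0.3 pattern in both groups.* DC scan rate = 0.1 × 0.6 + 0.9 × 0.3 = 0.33. Deformed among scanned DC = 0.06/0.33 = 0.18, mean 3.91 mm. Observed difference 5.50 − 3.91 = 1.59 mm, 36% too large. Scan rates are 40% v 33%.
- *Scanning unrelated to outcome in both groups.* Observed difference 1.17 mm, no bias.

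**Simulation.** There were 4000 runs per setting, with depth normal (SD 1) and scan probability logistic in depth. Group sizes for control/DC/DCR were 30/15/15, 60/30/30 and 120/60/60, with 30% or 50% scanned. The planned chi-square and a Kruskal–Wallis test on scanned breasts were applied at 0.05.

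| Setting | Chi-square not significant | Depth comparison |
|---|---|---|
| No true difference, random scanning | 95–97% | false positives about 5% |
| No true difference, depth-related in controls only, equal rates | 94–97% | spurious difference 0.23–0.34 SD (slope 0.5) to 0.53–0.77 SD (slope 1.5); false positives 7–22% to 23–87% |
| No true difference, same depth-related scanning in all groups | about 95% | difference about 0; false positives 4–5% |
| True difference 0.8 SD, same depth-related scanning in all groups | 40–88% | difference shrinks to about 0.67 SD |

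Slopes are log-odds of scanning per SD of depth. In the second row, restricting to runs that passed the check changes almost nothing: at 60/30/30, 30% scanned and slope 1, false positives are 30.7% overall and 31.0% given a pass.

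**Equality of rates.** A non-significant result does not establish equal scan rates either. For a two-group check of 40% v 60% scanned, power is 0.34, 0.59 and 0.88 at 30, 60 and 120 per group.

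**The case against.** Four counter-arguments deserve weight.

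- *The test can sometimes flag selection.* A reader might infer that the chi-square can never detect outcome-related scanning. That is too strong. When such scanning makes the rates unequal, the test may reject: it did so in 12–60% of runs in the last row of the table. It is blind when rates stay similar, and a rejection would not identify the cause.
- *No bias has been shown.* The documents give no reason for any scan. Routine follow-up imaging is as compatible with the text as imaging prompted by a contour problem. This stands, and it limits the point to an unguarded risk.
- *The SAP does not claim representativeness.* A reader might infer that the authors will treat a non-significant result as proof that the subset is sound. The text says only that the test will establish whether groups differ in MRI presence. Likewise, calling the study small has no support, because no sample size is given. The remaining gap is that the SAP does not rule such a reading out.
- *The further three-group comparison may help.* Because it directly follows the MRI sentences, it could mean a comparison of case mix within the MRI subset, which would be a partial safeguard. On either reading it compares groups with each other and does not compare scanned with unscanned breasts.

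**Conclusion.** The concern holds in this form: the one check aimed at the MRI subset does not compare scanned with unscanned breasts, so a biased sinking-depth comparison can pass it when scan rates are similar. The logic is secure. The size and direction are unknown.

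A reader might take 71% as the expected inflation. The documents do not support that: it comes from one assumed scenario with scanning related to outcome in controls only. Other assumptions give 36% inflation, no bias, or shrinkage. The change is worth making because the uninformative check can be supplemented cheaply from data already planned, not because the depth result is known to be wrong.

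**What to change.** Keep the group-by-MRI table as description and add to the SAP:

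1. Within each group, compare scanned with unscanned breasts on the blinded 6-month photographic deformity result, where photographs exist, and on recorded baseline factors. Compare prior radiotherapy only among controls, because it is constant by definition in DC and DCR. Report estimates whatever the p-value.
2. Report the photographic deformity comparison in all breasts with photographs and again in the MRI subset, so that a shift is visible.
3. State that a non-significant chi-square on MRI presence will not be taken as evidence that the subset is representative, and that the sinking-depth conclusion will be limited to scanned breasts if item 1 or 2 shows selection.

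Optionally, where the records hold the MRI indication, tabulate it by group. An analysis leaving out scans ordered for a contour or palpable finding should be exploratory only, because it selects on the outcome. Take the controls-only example, with a routine scan probability of 0.30 and a contour-prompted probability of 0.43 in deformed breasts, which together give 1 − 0.70 × 0.57 = 0.60. If contour-prompted scans displace routine ones, deformed controls keep a routine scan with probability 0.30 × 0.57 = 0.17. The remaining scanned controls are then 22% deformed (mean 4.11 mm), and the difference is 4.11 − 3.50 = 0.61 mm against a true 1.17 mm, about 48% too small. If routine scans are not displaced, the restriction recovers the true difference.

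The cost is SAP wording and a few extra tables, with no new patients, scans or readers. The within-group comparisons will be imprecise if groups are small.
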